Figure 2. Saphenous vein graft (SVG) and internal mammary artery (IMA) patency rates after CABG in VA Cooperative Studies #207/297/364.

SVG failure is critically important.

Mechanisms leading to saphenous vein graft failure

SVG failure is the result of 3 consecutive and inter-related processes: thrombosis, intimal hyperplasia, and atherosclerosis (Figure 3).^{11, 12} Immediately post CABG thrombus forms in SVGs due to endothelial disruption during harvesting and implantation. If the SVGs remain patent during this period, they develop a platelet-mediated progressive thickening of the vessel wall, which involves smooth muscle cell proliferation and extracellular matrix protein synthesis. Atherosclerosis subsequently develops on the ground of intimal hyperplasia, leading to decreased antegrade flow or eventually SVG occlusion.

[figure not shown]

Figure 3. Evolution of saphenous vein graft lesion development. After coronary artery bypass SVGs either occlude early or develop intimal thickening (panel 1), which forms the ground for moderate lesion development (panel 2). Moderate SVG lesions have high rates of progression to severe, symptom-causing lesions (panel 3), and eventually occlusion (panel 4).

SVG harvesting during CABG can cause significant injury, both at the time of removal from the leg and during SVG flushing to prepare the conduit for grafting.¹³ SVG wall injury may predispose to intraluminal platelet thrombus formation, which was observed in 68% of SVGs examined by OCT immediately post harvesting (Figure 4).¹³ Several factors may affect the severity of SVG injury, such as the mode of harvesting (endoscopic vs. open), manual high-pressure intraluminal distension, and the presence of baseline SVG disease. Lack

[figure not shown]

Figure 4. Identification of intraluminal thrombus formation in SVGs immediately after harvesting using optical coherence tomography (panel A) or by direct visualization (panel B).

of heparinization during SVG harvesting was associated with a trend for higher SVG occlusion rates one week post CABG, highlighting the risk for early SVG thrombosis.¹⁴

Several other factors are associated with decreased SVG patency, such as multiple distal SVG anastomoses¹⁵ and off-pump surgery,⁵ that is why SVGs with multiple anastomosis will be excluded from the present study; nearly all coronary bypass graft surgeries are performed on-pump at our institution.

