	0	1m +/- 5 days	3m +/- 10 days (phone FU)	6m +/- 10 days	9m +/- 10 days (phone FU)	12m +/- 30 days	
Inclusion/Exclusion criteria reviewed	X						
Informed consent	X						
Medical history	X	X	X	X	X	X	X
Physical examination/ Vital Signs	X	X		X		X	
Medication adherence		X	X	X	X	X	
Electrocardiogram	X					X	
SVG angiography, OCT, IVUS and NIRS						X	

FU=follow-up; SVG=saphenous vein graft; IVUS=intravascular ultrasonography; NIRS = near-infrared spectroscopy; OCT = optical coherence tomography

13. ANTICIPATED DATA AND DATA ANALYSIS:

Expected treatment effect

A recent study demonstrated the presence of thrombus in 25% of SVGs examined early post CABG.⁴⁷ Given the potent antiplatelet effect of prasugrel, we anticipate 80% reduction in the prevalence of thrombus in SVGs, as assessed by OCT.

Sample size calculation

Assuming that thrombus will be detected by OCT in 25% of patients in the placebo group vs. 5% of patients in the prasugrel group (80% relative reduction), the sample size required to detect the specified difference with 80% power and a 2-sided α

level of .05 is 48 patients per group, which was increased to 60 patients to allow for 20% dropout.

Assuming 48 patients are evaluable in each group, the power of the study assuming a prevalence of thrombus by OCT in the control arm of 20%, 25%, and 30% will be 67%, 80%, and 89%, respectively.

Enrolling 40 patients per year for three consecutive years will require enrollment of 25 % of the eligible patients at our institution. Enrollment rate in the SOS trial which also required angiographic and IVUS follow-up⁶² was 56%, suggesting that enrollment of the projected number of patients is feasible in our setting.

Statistical Analysis of primary endpoints

All endpoints (primary and secondary) will be analyzed with an intent-to-treat approach.

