The prevalence of thrombus within the target SVG at 12-month OCT imaging (primary efficacy endpoint) will be analyzed using the Fisher's exact test. In view of the relatively small sample size of the trial, multivariable logistic regression analyses will be performed to adjust the findings for any potential differences in the baseline characteristics of the two study groups, which are known to influence the occurrence of SVG failure. Such characteristics are: patient age, prior myocardial infarction; total cholesterol and HDL-cholesterol levels; minimum graft diameter; mean arterial pressure; ejection fraction; male gender; and current smoking.⁶⁹ The significant characteristics will be incorporated in the calculation of an adjusted odds ratio representing the association between treatment and the prevalence of thrombus, along with 95% confidence intervals. Because off-pump and endoscopic SVG harvesting may be associated with higher rates of SVG failure, randomization will be stratified by (a) on vs. off pump and (b) endoscopic vs. open harvesting.

The time elapsed to the incidence of severe bleeding, defined using the GUSTO criteria⁶⁷ (primary safety endpoint) will evaluated using Kaplan-Meier survival curves and compared between the 2 study groups using the log-rank test.

Statistical Analysis of secondary endpoints:

The differences in angiographic SVG failure, in total and normalized total SVG atheroma volume and in lipid core burden index at 12-month SVG imaging will be compared between the 2 study groups using Fisher's exact test. A logistic regression model will be developed to evaluate the treatment effect on this outcome adjusting for patient age, prior myocardial infarction; total cholesterol and HDL-cholesterol levels; minimum graft diameter; mean arterial pressure; ejection fraction; male gender; and current smoking.⁶⁹

The incidence of major adverse cardiovascular events (composite of death, acute coronary syndrome, and coronary revascularization) at 12 months will be compared between the two study groups using the chi-square test. Kaplan-Meier survival curves and the log-rank test will be used to compare time-to-event of major adverse cardiac events in the two study groups.

All tests will be two-sided. The critical level for the primary and four secondary outcomes will be 0.05. No adjustments will be made for multiple secondary endpoints

14. PROVISIONS FOR MANAGING ADVERSE REACTIONS:

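### The stated 67/80/89% power is not what the planned Fisher's exact test delivers at 48 per arm (about 57/72/84%), and the 25% control rate is not justified for a 12-month endpoint.

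*Combined protocol and SAP*

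**What the plan says.** Under Expected treatment effect, section 13 gives one source for the control rate: "A recent study demonstrated the presence of thrombus in 25% of SVGs examined early post CABG". It gives no imaging time point or method for that study. It then states: "we anticipate 80% reduction in the prevalence of thrombus in SVGs, as assessed by OCT".

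Under Sample size calculation, these become the design rates: "Assuming that thrombus will be detected by OCT in 25% of patients in the placebo group vs. 5% of patients in the prasugrel group". For 80% power with two-sided testing, the number needed at a significance "level of .05 is 48 patients per group, which was increased to 60 patients to allow for 20% dropout". With 48 evaluable per group, it states power for "a prevalence of thrombus by OCT in the control arm of 20%, 25%, and 30% will be 67%, 80%, and 89%, respectively".

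Under Statistical Analysis of primary endpoints, the quantity tested is "The prevalence of thrombus within the target SVG at 12-month OCT imaging (primary efficacy endpoint"), and the test named is Fisher's exact test. Sections 11 and 12 also place the imaging at 12 months after surgery.

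**The concern.** There are two gaps between the power statement and the analysis it should describe.

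**The test.** Fisher's exact test is conservative in samples this small with low event rates. A power figure from a normal approximation without continuity correction overstates what it can deliver.

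**The control rate.** The only rate offered is described as early post-CABG, while the endpoint is read at 12 months. Section 13 carries the figure across without comment and then varies it by only five points either way.

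The stake is how a non-significant result will be read. Against a claimed 80% power it would look like fair evidence against the hypothesised effect. If the true power is nearer 72%, or lower still if the 12-month rate is below 20%, that reading is too strong.

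**Working it through.** **Inputs** (sections 12 and 13): control rate p1 = 0.25; prasugrel rate p2 = 0.05; two-sided α = 0.05; 80% power; 1:1 allocation; 48 evaluable per arm; 20% dropout; one graft per patient, so a per-graft rate can serve per patient.

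**Step 1. Reproduce the stated size.** Pooled-variance normal approximation, with p̄ = (p1 + p2)/2 = 0.15:

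n = [1.960·√(2p̄(1−p̄)) + 0.8416·√(p1(1−p1) + p2(1−p2))]² / (p1−p2)²

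= [1.960·√0.255 + 0.8416·√0.235]² / 0.04 = (0.990 + 0.408)² / 0.04 ≈ 48.8

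This rounds up to 49, against the stated 48. Dropout: 48/(1 − 0.20) = 60, as stated.

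**Step 2. Reproduce the stated power.** Same approximation, n = 48:

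power = Φ{[(p1−p2)√n − 1.960·√(2p̄(1−p̄))] / √(p1(1−p1) + p2(1−p2))}

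At 25% versus 5%: (0.20 × 6.928 − 0.990)/0.485 = 0.817, so power is 79%. With the 80% reduction held, control rates of 20, 25 and 30% give 68, 79 and 88%, within two points of the stated 67, 80 and 89%. Fixing prasugrel at 5% instead gives 61, 79 and 91%, which does not match. The plan's line therefore holds the relative reduction constant and does not reflect Fisher's test.

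**Step 3. Apply the planned test.** Exact power is the sum of Bin(i; 48, p1) × Bin(j; 48, p2) over all tables (i, j) with two-sided Fisher p ≤ 0.05. As an illustration of its strictness, with no thrombus on prasugrel, 5 events on placebo give p = 0.056 and 6 give p = 0.026.

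| Control rate | Prasugrel rate (80% reduction) | Stated power | Normal approximation | Fisher's exact |
|---|---|---|---|---|
| 10% | 2% | not given | 38% | 17% |
| 15% | 3% | not given | 54% | 38% |
| 20% | 4% | 67% | 68% | 57% |
| 25% | 5% | 80% | 79% | 72% |
| 30% | 6% | 89% | 88% | 84% |
| 35% | 7% | not given | 93% | 91% |

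For 25% versus 5%, Fisher's test first reaches 80% power at 55 evaluable per arm (80.1%).

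**Step 4. Keep the two effects apart.** At the plan's own 25%, the test alone moves power from the stated 80% to 72%, with no question about timing. Movement up or down the rows is the effect of the control rate, for which the documents give no 12-month value. The 10, 15 and 35% rows are assumptions.

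**Step 5. Smaller reductions, as assumptions.** Control 25%, 48 per arm, Fisher's test: a 60% reduction (25% to 10%) gives 39%; 50% (to 12.5%) gives 26%; 40% (to 15%) gives 16%.

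**The case against.** The best defence is that the power line is conditional. It states what power would be if control-arm OCT prevalence in this trial were 20, 25 or 30%, and under the approximation used the arithmetic is right. The word early is also loose in this protocol: section 6 calls failure after one year late, and section 7 counts early failure over the first postoperative year, so the source study may have imaged near 12 months. Finally, this is an abbreviated protocol that refers to an attached sponsor's protocol, where a justification may exist. All of this stands. It limits the timing point to a missing justification, and a sentence giving the source's time point might settle it. It does not touch the mismatch with the planned test.

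A reader might go further and infer that the 12-month rate must lie below 25%. Section 6 says "Immediately post CABG thrombus forms in SVGs due to endothelial disruption during harvesting and implantation", and it reports thrombus in 68% of grafts straight after harvesting, against 25% later. The documents do not support that inference. The two percentages come from different studies, and the second has no stated timing or method, so they are not a time trend. Section 6 also calls the graft processes inter-related and gives thrombus a part in later graft atherosclerosis.

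A reader might also infer from Table 1 that no comparable drug has cut graft closure by more than about half. Table 1 does not show that. In the ticlopidine trial at day 10, closure falls from 33.3% to 15.6%, which is 17.7/33.3 = 53%. In the 30-day clopidogrel trial, radial graft occlusion falls from 43.8% to 10.5%, which is 33.3/43.8 = 76%. Those are other drugs, partly another conduit, and closure rather than OCT thrombus. Table 1 neither supports nor rules out 80%.

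**Conclusion.** The point holds in two parts of different strength.

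The power line is wrong for the planned analysis. With the plan's own rates and 48 evaluable per arm, Fisher's exact test gives about 57, 72 and 84%, not 67, 80 and 89%: a shortfall of about 10, 8 and 5 points. This rests only on the stated inputs and the named test. At the design rates, the chance of missing the hypothesised effect is about 28% rather than 20%.

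The 20 to 30% control range is unsupported for the 12-month endpoint. It would be going too far to say that the range cannot describe this endpoint: it does if the 12-month rate falls inside it. The documents do not show that the rate lies outside, or on which side. Across an assumed 10 to 35%, with the 80% reduction held, Fisher power runs from 17% to 91%, so the unverified rate matters more than the choice of test.

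**What to change.** In section 13:

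1. Restate power at 48 per arm using Fisher's exact test: 57, 72 and 84% at control rates of 20, 25 and 30% with an 80% reduction.
2. State when after surgery the grafts in the 25% source were imaged, and say that the 12-month control rate is an assumption unless that source or another supports it.
3. Widen the sensitivity range in both directions, for example 10% (17%), 15% (38%), 20% (57%), 25% (72%), 30% (84%) and 35% (91%).
4. Add rows for a smaller relative reduction, for example 60% and 50% at a 25% control rate (39% and 26%), labelled as assumptions.

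The cost is a few lines of text and a less favourable stated power. No extra patients are needed to make the statement accurate. If the sponsor preferred to keep a true 80% at 25% versus 5%, about 55 evaluable per arm would be required, or 55/0.80 = 68.75, so 69 randomised per arm rather than 60. That is a separate decision and not part of this fix.

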For safety monitoring, any emergency adverse event resulting from participation in the study will be treated at the Dallas VA Medical Center. [name] will evaluate all adverse events and determine the appropriate course of action.

If a patient develops severe bleeding during the study period, prasugrel will be temporarily held and will be discontinued if the patient is considered to be at increased risk for recurrent bleeding. If a patient develops an indication for receiving oral anticoagulation therapy with warfarin or dabigatran during his or her participation in the study, prasugrel administration will be discontinued to minimize the risk of bleeding.

If any subjects are hospitalized for an acute coronary syndrome or undergo coronary angiography at an outside hospital, the hospitalization records will be obtained and reviewed by the clinical events committee. The Universal definition of myocardial infarction will be used for diagnosing myocardial infarction. Bleeding will be assessed with the use of the GUSTO criteria.⁶⁷ Severe bleeding will be defined as fatal bleeding, intracranial hemorrhage, or bleeding causing hemodynamic compromise requiring blood or fluid replacement, inotropes, or surgery.⁶⁷ The frequencies of moderate bleeding, defined as bleeding requiring transfusion not characterized as severe, and moderate/severe and severe bleeding will also be analyzed. Information on (surgical or percutaneous) coronary revascularization will also be collected. Data will be entered on paper-based case report forms and will be double-entered into a secure, password protected database, accessible only by study personnel. Subjects will be identified by a unique study number in the database.

Additionally a Data Safety Monitoring Board will be appointed to review the study periodically (every 12 months, or sooner if required).

15. RISK/ BENEFIT ASSESSMENT:

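### The stated 80% power applies the full potency-based effect (25% to 5%) to an intent-to-treat comparison and leaves no margin for scanned patients who are off prasugrel

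*Combined protocol and SAP*

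**What the plan says.** All of the sizing is in Section 13 of the combined protocol and SAP.

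- **Effect size (Expected treatment effect).** A study of vein grafts early after surgery found thrombus in 25%. The expected effect is then stated: "Given the potent antiplatelet effect of prasugrel, we anticipate 80% reduction in the prevalence of thrombus in SVGs, as assessed by OCT". Potency is the only reason given for its size.
- **Sample size.** The rates that enter the calculation are given as follows: "Assuming that thrombus will be detected by OCT in 25% of patients in the placebo group vs. 5% of patients in the prasugrel group". For 80% power at a two-sided alpha of 0.05, the plan requires 48 in each arm. Of that number it then says: "which was increased to 60 patients to allow for 20% dropout".
- **Power sensitivity.** Power is put at 67%, 80% and 89% for control rates of 20%, 25% and 30%, in a sentence that begins: "Assuming 48 patients are evaluable in each group, the power of the study assuming a prevalence of thrombus by OCT in the control arm". Nothing else is varied.
- **Analysis set (Statistical Analysis of primary endpoints).** The rule is: "All endpoints (primary and secondary) will be analyzed with an intent-to-treat approach". The primary test is Fisher's exact test.

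Three other places bear on who is taking drug at the scan:

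- Section 12 (Randomization and Treatment) provides pill counts, and counselling when compliance is under 80%.
- Section 14 has prasugrel held after severe bleeding and discontinued if the patient is thought likely to bleed again. If oral anticoagulation becomes necessary, "prasugrel administration will be discontinued to minimize the risk of bleeding".
- Section 12 (catheterization and imaging) and Table 2 schedule the 12-month scan and state no exception for patients who have stopped drug.

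**The concern.** Potency describes what the drug does in patients who take it. An intent-to-treat comparison measures what happens to everyone assigned to it. The two rates coincide only if every scanned prasugrel patient stays on drug, or if those who stop lose none of the benefit. The plan moves from one to the other without a stated discount.

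The 20% allowance does not supply that discount on its natural reading. It takes 60 per arm down to 48, and the next sentence computes power for 48 evaluable patients. It therefore replaces patients without a usable scan. A patient who stops drug but is still scanned stays in the prasugrel arm and pulls its thrombus rate towards the placebo rate.

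What is at stake is how a non-significant result would be read. If the trial was presented as having 80% power but the intent-to-treat contrast was smaller than 25% against 5%, readers would take a null result as stronger evidence against prasugrel than it is.

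**Working it through.** **Inputs from the documents:** placebo rate 25%, prasugrel rate 5%, two-sided alpha 0.05, 1:1 allocation, 48 evaluable and 60 randomized per arm, Fisher's exact test.

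**Assumed, because the documents give no figure:** the share *d* of scanned prasugrel patients who are off drug, and the thrombus rate in those patients.

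**1. Reproduce the plan.** The pooled normal approximation without continuity correction is

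n = [1.96·√(2p̄(1−p̄)) + 0.842·√(p₁(1−p₁)+p₂(1−p₂))]² / (p₁−p₂)².

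With p₁ = 0.25, p₂ = 0.05 and p̄ = 0.15, n = 48.8, or 49 per arm against the stated 48. The dropout step is 48/(1−0.20) = 60, as stated.

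The matching power formula is Φ{[|p₁−p₂|√n − 1.96·√(2p̄(1−p̄))] / √(p₁(1−p₁)+p₂(1−p₂))}. At n = 48 with a constant 80% reduction it gives 68.0%, 79.3% and 87.7% for control rates of 20%, 25% and 30%, against the stated 67%, 80% and 89%. The plan's figures therefore follow from the full contrast with nothing held back.

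**2. Dilute the prasugrel arm.** If off-drug patients revert fully to 25%, the intent-to-treat rate is 0.05(1−d) + 0.25d:

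| Off drug (assumed) | Prasugrel-arm rate | Approx. power, 48 scanned | Approx. power, 60 scanned | Fisher exact power, 48 scanned | Fisher exact power, 60 scanned |
|---|---|---|---|---|---|
| 0% | 5% | 79.3% | 87.6% | 72.2% | 84.5% |
| 5% | 6% | 73.7% | 82.9% | 65.2% | 78.3% |
| 10% | 7% | 67.7% | 77.4% | 58.1% | 71.4% |
| 20% | 9% | 55.2% | 64.9% | 44.7% | 56.7% |

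Fisher power is the sum of binomial probabilities over all pairs of counts for which the two-sided Fisher p-value is at most 0.05.

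**3. Milder assumption.** If off-drug patients keep half the benefit, their rate is 15%. At 10% off drug the arm rate is 0.9×5% + 0.1×15% = 6%, so approximate power at 48 per arm is 73.7%. At 20% off drug the arm rate is 7% and power is 67.7%.

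**4. The alternative reading.** Suppose 5% is already the intent-to-treat rate and off-drug patients revert to 25%. The on-drug rate must then be (0.05 − 0.25d)/(1−d). At 10% off drug this is 0.025/0.90 = 2.8%, an 89% reduction. At 20% it is 0/0.80 = 0%, a complete reduction.

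**The case against.** The best reply is that nothing has been miscalculated. The plan's figures reproduce. It states group rates, which are what an intent-to-treat comparison uses, and the potency sentence may only explain why a large group effect is expected. Dropout is undefined and could include stopping drug. The stopping rules in Section 14 are narrow, and bleeding-prone and anticoagulated patients are excluded at entry. The protocol provides for compliance under 80% but does not forecast it. This is also an abbreviated protocol that refers to an attached sponsor's protocol, where adherence assumptions may appear.

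Much of this stands. That 5% is an on-drug rate, and that the allowance covers missing scans only, are inferences. The size of any loss cannot be fixed, and full reversion to 25% is the pessimistic end.

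It does not remove the point. The text does not say that 5% is net of non-adherence, and if it is, the implied on-drug effect exceeds 80% as soon as anyone scanned has stopped and lost benefit. If dropout was meant to include stopping, replacing such patients one for one does not undo dilution. Even with all 60 scanned, approximate power falls below 80% somewhere between 5% and 10% off drug, and nothing is then left for missing scans.

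A reader might go further and infer three things that the documents do not support:

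- *That 80% power holds only if no scanned patient stops drug.* With 60 scanned per arm, approximate power is still 82.9% at 5% off drug. Under Fisher's test at 48 per arm, power is 72.2% even with nobody off drug.
- *That true power is 55%, or any other single figure.* No discontinuation rate is given.
- *That a complier-average analysis of the pill counts would show whether a null result came from discontinuation.* Such an estimate rescales the intent-to-treat difference, so its test is essentially the same test, and partial compliance strains its assumptions.

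**Conclusion.** The point holds as a gap in a stated assumption, not as an arithmetic error. The power paragraph rests on a potency-based effect applied undiluted to an intent-to-treat comparison, and its sensitivity figures never vary that assumption.

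The direction is clear: if 5% is the on-drug rate, any scanned patient who is off drug and loses benefit lowers power from a calculation that has no slack at 48 evaluable. The size is conditional on the off-drug share, how much benefit is lost, and how many patients are scanned. Over assumed shares of 0% to 20% with full reversion, the planned test has about 72% down to 45% power at 48 per arm. The part of this due to the choice of test (79% to 72% with nobody off drug) is separate from dilution. Open-label antiplatelet use in the placebo arm would dilute the contrast further and is not quantified here.

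**What to change.** Keep 120 patients, and keep intent-to-treat as the primary analysis. In Section 13:

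1. State whether 5% is the rate expected on drug or the net intent-to-treat rate, and what dropout includes. If 5% is net, give the on-drug effect and the off-drug share that it implies.
2. Extend the power paragraph with a range over the off-drug share, labelled as an assumption. State how much benefit off-drug patients are assumed to keep, and show both 48 and 60 scanned per arm.
3. Report these figures under Fisher's exact test, since that is the planned analysis: about 72/65/58/45% at 48 per arm and 85/78/71/57% at 60 per arm, for 0/5/10/20% off drug with full reversion.

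A complier-average estimate may be added as an optional, descriptive result. Whether patients who stop drug are imaged at 12 months is implied by intent-to-treat and the schedule but not stated. The sponsor should reconcile Section 12, Table 2, Section 13 and Section 14 on this; no clinical rule is proposed here.

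The cost is a few sentences and one small table. The downside is that the stated power becomes less favourable.

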Approximately 120 patients will be randomized into this study at the Dallas VA Medical Center.

10. JUSTIFICATION FOR THE USE OF SPECIAL SUBJECT POPULATIONS:

Not applicable.

11. STUDY DESIGN:

The primary efficacy objective is to compare the prevalence of SVG thrombus as detected by optical coherence tomography of a target SVG between patients receiving prasugrel vs. placebo. We hypothesize that prasugrel will be superior to placebo in reducing the prevalence of SVG thrombus at 12-month follow-up OCT imaging.

The primary safety endpoint is the incidence of severe bleeding as defined using the GUSTO study criteria.⁶⁷ We hypothesize that patients receiving prasugrel will have similar incidence of severe bleeding compared to patients receiving placebo during the 12-month study period.

The secondary endpoints will be: (1) incidence of angiographic SVG failure (defined as $\geq 75\%$ SVG diameter stenosis in at least one SVG); the total and normalized total SVG atheroma volume within at least 40 mm of the target SVG, as assessed by intravascular ultrasonography; the lipid core burden index of the target SVG, as assessed by near-infrared intracoronary spectroscopy; and (2) the incidence of major adverse cardiac events and moderate bleeding during the 12-month study period.

The proposed study is a phase 3, single-center, randomized, double-blind, controlled, parallel-group study of prasugrel vs. matching placebo in patients with recent CABG, starting at the time of hospital dismissal from CABG (Figure 13). All patients will be receiving aspirin, as per standard current practice.

[figure not shown]

Figure 13: Flowchart of the proposed study design.

CABG = coronary artery bypass graft surgery; OCT = optical coherence tomography; IVUS = intravascular ultrasound; NIRS = near-infrared spectroscopy; R = randomization; m = month; FU = follow-up.

12. DESCRIPTION OF PROCEDURES TO BE PERFORMED:

The study design will be explained to the patients and if they agree to participate they will be asked to sign an informed consent form and they will receive a copy of the consent form. They will subsequently be randomized to prasugrel or placebo, as described below.

Randomization and Treatment

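### The stated power of 67%/80%/89% with 48 evaluable patients per group is not that of the planned Fisher's exact test, which has about 57%/72%/84%

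*Combined protocol and SAP*

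**What the plan says.** The sample size paragraph of section 13 plans for thrombus on OCT in 25% of placebo and 5% of prasugrel patients, an 80% relative reduction, at a two-sided level of 0.05. It states that "the sample size required to detect the specified difference with 80% power" "is 48 patients per group, which was increased to 60 patients to allow for 20% dropout". Section 9 agrees: "Approximately 120 patients will be randomized into this study".

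The next paragraph gives a sensitivity statement. "Assuming 48 patients are evaluable in each group", power for a thrombus prevalence in the "control arm of 20%, 25%, and 30% will be 67%, 80%, and 89%, respectively". Neither paragraph names the test or formula behind these figures.

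The test appears under Statistical Analysis of primary endpoints, where the sentence on 12-month OCT thrombus reads "primary efficacy endpoint) will be analyzed using the Fisher's exact test". The section closes with "All tests will be two-sided. The critical level for the primary and four secondary outcomes will be 0.05".

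**The concern.** Power belongs to a particular test. Fisher's exact test is conservative with small samples and low event rates, because the discrete p-value keeps its real type I error below the nominal 5%. A sample size from an uncorrected normal approximation, or from a less conservative test, therefore overstates what Fisher's test can do.

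The assumed 80% reduction is already large, so the design has little room to absorb a loss of power. If the stated power is too high, the funder, the monitoring board and later readers would judge a null result against a type II error of 20% that the planned analysis does not have.

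**Working it through.** **Inputs, all from section 13 unless noted.** Rates 25% and 5%; two-sided level 0.05; 48 evaluable per group; 1:1 allocation (section 12); dropout 20%; Fisher's exact test. For control rates of 20% and 30% the plan gives no prasugrel rate. I keep the 80% reduction, giving 4% and 6%. The stated figures fit only this reading: under the pooled normal formula a fixed 5% prasugrel rate would give 61/79/91%, and a fixed 20-point difference 92/79/69%.

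**Step 1. Reproduce the plan's figures.** Pooled normal formula without continuity correction:

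n = [1.960·√(2·0.15·0.85) + 0.842·√(0.25·0.75 + 0.05·0.95)]² / 0.20² = (0.990 + 0.408)² / 0.04 ≈ 48.8, so 49.

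Power at n = 48: Φ[(0.20·√48 − 0.990)/0.485] = Φ(0.817) = 79.3%. The other two rates give 68.0% and 87.7%. All are within about one patient or 1.3 points of the stated values. A doubled one-sided mid-p test gives 67.4/80.3/89.1%, which rounds to the stated figures. The plan does not say which method was used, and neither is Fisher's exact test. The dropout step is correct: 48/0.8 = 60.

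**Step 2. Power of the named test.** Sum over all pairs of counts (x placebo, y prasugrel):

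Power = Σ Bin(x; n₁, p₁)·Bin(y; n₂, p₂)·1{Fisher p(x, y) ≤ 0.05}.

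The two-sided p can be probability-ordered (all tables no more likely than the one observed) or twice the smaller one-sided tail. With equal arms the two coincide. As an example of the conservatism, 5 versus 0 events at 48/48 gives p = 2·C(48,5)/C(96,5) = 0.056, not significant; 6 versus 0 gives 0.026.

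| Setting | 20% vs 4% | 25% vs 5% | 30% vs 6% |
|---|---|---|---|
| Stated, 48/48 | 67% | 80% | 89% |
| Fisher, 48/48 | 56.6% | 72.2% | 83.6% |
| Shortfall (points) | 10.4 | 7.8 | 5.4 |
| Fisher, 60/60 (no dropout) | 71.6% | 84.5% | 92.2% |

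Maximum type I error at 48/48 is 3.2%.

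**Step 3. What would give 80%.** At 25% versus 5% with equal arms, 54 per arm gives 79.1% and 55 gives 80.1%. Keeping 55 of 60 allows dropout of at most 1 − 55/60 = 8.3%, against the planned 20%. At 48/48 the test reaches 80% only with a larger effect: a prasugrel rate of about 3.85% against 25% (reduction 1 − 0.0385/0.25 ≈ 85%), or a control rate of about 28% with the 80% reduction.

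**Step 4. Unequal arms after dropout.** Let the evaluable number in each arm be Binomial(60, 0.8), independently, and average the power:

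| Two-sided p | 20% vs 4% | 25% vs 5% | 30% vs 6% |
|---|---|---|---|
| Probability-ordered | 63.6% | 77.2% | 86.6% |
| Doubled one-sided | 59.3% | 73.7% | 84.2% |

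Both remain below the stated figures at all three rates.

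**The case against.** The strongest reply is that 72% is special to exactly equal arms. With the probability-ordered p-value, 48 placebo and 49 prasugrel patients give 66.7/79.7/88.6%, almost the stated figures, and 47 and 50 give 80.8% at 25% versus 5%. That is true, and 72% should not be read as the power the trial will most probably have. But the gain is erratic: 49 placebo and 47 prasugrel give 74.9%, and with the doubled p-value 47 and 49 give only 73.6%. Averaged over dropout, the shortfall at 25% versus 5% is about 3 points (probability-ordered) or 6 points (doubled). The plan's own statement is for 48 in each group, so equal arms are the right comparison for it.

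Second, the figures are sound for a normal approximation, so nothing was miscalculated. This stands as a description: the fault is a mismatch between planning method and analysis test. It does not rescue the figures, because section 13 names Fisher's test for this endpoint and reserves the chi-square test for major adverse cardiovascular events.

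Third, 60 per arm are randomized, and with all evaluable the power is 84.5%. But the 12 extra per arm are there to be lost to the planned dropout, and the stated power is explicitly for 48.

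Fourth, the document is an abbreviated protocol and points to a sponsor's protocol, not seen here, that may give the power method. That could explain the figures but would not make them apply to Fisher's test.

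Finally, the plan already shows power from 67% to 89% across control rates, a wider spread than this gap, and it will report an odds ratio with a confidence interval. Both points limit the harm. Neither makes the stated power correct.

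**Conclusion.** The concern holds. For the named test at 48 evaluable per group, power is 56.6/72.2/83.6% against the stated 67/80/89%, and 48 per group does not give 80% power. At the design effect the type II error is 27.8%, not 20%; at a 20% control rate it is 43.4%, not 33%. The 25% versus 5% result rests only on stated inputs. The 20% and 30% results assume a constant 80% reduction, and the dropout averages assume independent 20% dropout in each arm.

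This should be corrected, but it does not threaten validity: the test controls type I error, and the planned 120 patients may still give adequate power if dropout is well below 20%.

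**What to change.** Keep Fisher's exact test and the planned 120 patients, and change the text of section 13:

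1. Under Statistical Analysis of primary endpoints, state whether the two-sided p-value is probability-ordered or twice the one-sided tail. The choice matters once the arms are unequal.
2. Under Sample size calculation, restate power for Fisher's test at 48 evaluable per group as about 57%, 72% and 84%, and say that the 80% relative reduction is held at each control rate.
3. Stop describing 48 as the size required for 80% power. Say that 48 per group gives about 72% at 25% versus 5%, that 55 per group are needed for 80% if the arms are equal, and that 60 evaluable per group would give about 72%, 85% and 92%. The dropout-averaged 77% or 74%, matching the chosen p-value, can be quoted beside the 72%.

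This costs nothing in patients, visits or data. The only downside is a less favourable stated power.

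The team may instead name a less conservative test before unblinding and quote its own power, but this is optional. At 48/48, Boschloo's test gives about 65/78/87% with size held below 5%. Doubled one-sided mid-p gives 67/80/89%, but its maximum size is about 5.2%.

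For comparison only, holding 80% power with Fisher's test and 20% dropout would take 55/0.8 = 68.75, so 69 randomized per arm (138 in all) if 55 per arm must remain. Averaged over random dropout it would take 64 per arm (probability-ordered) or 68 per arm (doubled), 128 or 136 in all.
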